7.5 Adverse Event Reporting

Information regarding AEs will be derived by questioning the participants in an unbiased, general query (e.g., "How do you feel?" or "How have you been feeling since your last clinic visit?"), by subjects' spontaneous reports, or by observation.

AEs will be recorded in the source documents. All AEs will then be transcribed into the CRF.

For each sign, symptom or adverse event, the following information will be recorded in the CRF:

- a brief descriptor of the adverse event
- severity (mild/ moderate/ severe)
- whether the AE was "serious" or not (as defined in the serious adverse event section)
- frequency (single occurrence/ intermittent/ continuous)
- outcome (resolved/ resolved with sequelae/ improving/still present and unchanging/ death
- whether any treatment was administered for the AE.

In the event of a SAE, whether related to study drug or not, the Investigator or representative must make an accurate and adequate report consisting of at least the minimum criteria (Site and Subject ID, Date site became aware of the event, SAE Term, Seriousness criteria, Study Drug information, Investigator/Reporter and site address) within 24 hours after the site became aware by email, fax, or telephone to Biorasi Safety and Pharmacovigilance team will complete the SAE report onto a MedWatch 3500A form for evaluation and convey for review by the Medical Monitor and Sponsor contact. Accurate Completion of the MedWatch 3500A form will consist of all data supplied such as Subject's demography, SAE narrative, concomitant medication, laboratory parameters and relevant medical history.

Copies of each report with the associated documentation (i.e., queries, medical records, lab records,

Confidential Page 43 of 59

IRB/IEC communications and all source documents) will be kept in the site's study file.

A subject experiencing one or more SAEs will receive treatment and follow-up evaluations by the Investigator or may be referred to another appropriate physician for treatment and follow-up. The Investigational Site will be responsible for collection and forwarding follow-up SAE information to the Biorasi Safety and Pharmacovigilance.

MEDICAL MONITOR

[name] Medical Monitor Biorasi Safety and Pharmacovigilance email: [contact]

[name]

[name] [contact]

7.6 Reporting of Pregnancies

If a subject becomes pregnant during the participation in the study, the Investigator will immediately discontinue the patient from the study and contact the Medical Monitor, Biorasi Safety Team, and the Sponsor. Diligent efforts will be made to determine the outcome for all pregnancy exposures in the clinical trial. Information on the status of the mother and the child will be forwarded to the Biorasi Safety Team using the Pregnancy Data Collection Form. Generally, follow-up will occur within 6 to 8 weeks following the estimated delivery date. Any premature termination of the pregnancy will be reported. Detailed guidance on the reporting of Pregnancies will be provided in the SAE and Pregnancy Reporting Guidance.

7.7 Unblinding due to SAE

Patients, Investigators, site staff, Hyloris Developments SA and Biorasi will be blinded to treatment assignment.

Reasons to unblind patient should be clearly documented in subject notes, and the monitoring site visit report. In the event of an emergency necessitating unblinding the PI/site staff will make every effort to contact and discuss the event with the Medical Monitor prior to unblinding.

Treatment assignment for an individual subject should be unblinded only in an emergency by the Investigator, when knowledge of the treatment assignment is urgently needed for the clinical management or welfare of the subject. Treatment should be provided in accordance with the medical condition and according to the information provided in the Investigator's Brochure.

According to the FDA guidance *Safety Assessment for IND Safety Reporting* IND safety reports submitted should be unblinded. If the blind is broken and a subject with an adverse event that would meet the criteria for reporting as a single event was receiving placebo, the event will not be reported in an IND safety report because there is a reasonable possibility that the drug did not cause the adverse event. However, if the SAE is determined to be from drug exposure reporting to the FDA will take place.

Confidential Page 44 of 59

The Investigator must document the breaking of the code, and the reasons for doing so on the CRF, in the site file, and in the medical notes.

The Investigator must notify the Sponsor in writing as soon as possible following the code break detailing the necessity of the code break. Subject always to clinical need and where possible, all other members of the research team should remain blinded.

Confidential Page 45 of 59

8 DATA ANALYSIS

The sections below summarize the intended statistical methods and analyses of data for the study. A more detailed statistical analysis plan will be written prior to finalization of the clinical trial database. Any changes to the planned methods and analyses will be described and justified in the protocol and/or in the final clinical study report, as appropriate.

Descriptive statistical methods will be used to summarize the data from this study, with confidence intervals calculated for the primary efficacy endpoints. Unless stated otherwise, the term "descriptive statistics" refers to number of subjects (n), mean, median, standard deviation (SD), minimum, and maximum for continuous data and frequencies and proportions for categorical data. The term "treatment group" refers to randomized treatment assignment: active-test and active-reference. All data collected during the study will be included in data listings. Unless otherwise noted, the data will be sorted first by treatment assignment, subject number, and then by date within each subject number.

Unless specified otherwise, all statistical testing will be two-sided and will be performed using a significance (alpha) level of 0.05.

All statistical analyses will be conducted with the SAS® System, version 9.4 or higher.

8.1 Subject Population/Data Sets to Be Evaluated

The subject populations are defined as follows:

- 1. Safety Population: The safety population includes all randomized subjects who received and used study product.
- 2. **Modified Intent-to-Treat (mITT) Population:** A modified intent-to-treat population includes all subjects who are randomized, applied at least one dose of assigned product, and returned for at least one post-baseline evaluation visit.
- 3. **Per Protocol (PP) Population:** all randomized subjects who met all inclusion/exclusion criteria, had no protocol violations that would affect the treatment evaluation, were compliant with applying study product, and returned to the study site for the primary endpoint evaluation at four days (± 5 days) after the last day of the last cycle of treatment. Compliant subjects are defined as those who used at least 75% and no more than 125% of study drug doses until treatment success or four cycles of treatment.

Subjects discontinuing due to "treatment failure" will be included in the PP population analysis as treatment failures, and will have alternative treatment recommended by the Investigator. Subjects discontinued prematurely from the study for any other reason (i.e., noncompliance, or withdrawal of consent, etc.) will be excluded from the PP population, but included in the mITT population, using Last Observation Carried Forward (LOCF).

The results in the PP population will be considered definitive for therapeutic equivalence with those in the mITT population considered supportive. The results in the mITT population will be considered definitive

Confidential Page 46 of 59

for superiority of each active treatment to placebo with those in the PP population considered supportive. Safety analyses will be performed using the Safety population.

8.2 Sample Size Determination

The difference in the proportion of subjects in the test and reference treatment groups who achieve "treatment success" defined as "total disappearance of all warts within all treated areas" at four days (\pm 5 days) after the last day of the last cycle of treatment will be evaluated using a two-sided 90% confidence interval. The therapeutic equivalence of the test and reference products will be established if the confidence bounds of the 90% confidence interval are contained within the limits of -0.20 to +0.20. The results in the PP population will be considered definitive for therapeutic equivalence with those in the mITT population considered supportive.

Table 5. Sample Size Rationale

Equivalency margin	Power (%)	CI (%)	Sample Size mITT* (test: RLD: placebo)	Sample Size PP* (test: RLD: placebo)	
20%	85%	90%	392 (168:168:56)	350 (150:150:50)	

^{*} Sample sizes were calculated assuming: 40.0% success rate for active treatment, and 15.0% success rate for vehicle; 20% equivalency margin (EQ).

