	Study visits will occur on the seventh (7) day of each treatment cycle: on Day 7 (Week 1), Day 14 (Week 2), Day 21 (Week 3), and Day 28 (Week 4). Primary endpoint (total disappearance of all treated warts) will be evaluated during each of these visits. In case the primary endpoint is reached at any of the visits prior to the Day 28 visit, it will be considered as End of Study (EOS) visit – the Investigator will perform physical examination and repeat urine pregnancy test, and subject's participation will be considered complete. If total disappearance of warts is not achieved, a new treatment cycle will be initiated for a maximum of four cycles in total for the subject.
	During each study visit, the Investigator will collect vital signs, evaluate EAWs for absence or present, capturing the count of EAWs, record Local Application Site Reactions and adverse events (AEs), assess Patient's Diary Card completion and subject's compliance with the study drug application, review concomitant medication and confirm that there were no prohibited therapies applied from the last visit.
	In the event the primary endpoint (total disappearance of all warts within all treated areas) has been achieved prior to the Day 28 visit, this visit will be considered End of Study (EOS) visit. In case a subject discontinues prematurely, the Investigator will conduct an Early Termination (ET) visit, capturing the reason for discontinuation and performing assessments of EOS visit.
Number of Subjects and Sites	The planned overall sample size for this clinical trial is approximately 413 adult male and female subjects with external anogenital warts, who will be randomized at a 3:3:1 ratio (test:RLD:placebo) at about 16 clinical research centers in the United States, Russia and Ukraine. mITT and PP population size will be approximately 392 and 350 correspondingly.
Eligibility Criteria	Subjects who satisfy ALL of the following inclusion and have NONE of the following exclusion criteria may be enrolled in the study:
	INCLUSION CRITERIA
	 Willing and able to provide written informed consent prior to participating in this study. Male or female subjects, aged 18-65 inclusive, with a clinical diagnosis of external anogenital warts (i.e., perianal warts and/or external genital warts), including two or more distinct external genital

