	The difference in the proportion of subjects in the test and reference treatment groups who achieve "treatment success" defined as "total disappearance of all warts within all treated areas" at four days (\pm 5 days) after the last day of the last cycle of treatment will be evaluated using a two-sided, continuity-corrected 90% confidence interval. The therapeutic equivalence of the test and reference products will be established if the confidence bounds of the 90% confidence interval are contained within the limits of -0.20 to +0.20. The results in the per-protocol (PP) population will be considered definitive for therapeutic equivalence with those in the modified Intent-To-Treat (mITT) population considered supportive.
	Superiority will be assessed through continuity-corrected Z-tests comparing each active treatment to placebo. If both the test and RLD success proportions are statistically significantly greater than the placebo proportion (p<0.05, two-sided) then they will be considered to be superior to the placebo. The results in the mITT population will be considered definitive for superiority with those in the PP population considered supportive.
	Subjects discontinuing due to "treatment failure", defined as worsening of condition and requiring alternate or supplemental therapy for the treatment of external anogenital warts during the study, will be included in the PP population analysis as treatment failures, and provided with effective treatment. Subjects discontinued prematurely from the study for any other reason (i.e., noncompliance, or withdrawal of consent, etc.) will be excluded from the PP population, but included in the mITT population, using Last Observation Carried Forward (LOCF).
	SAFETY ANALYSIS

Protocol: 16-POD-001 Version 2.0, 15-Jan-2018

Safety data analysis will include local application site reaction scores (erythema, dryness, burning/stinging, erosion, edema, pain, itching and bleeding), reported adverse events, vital signs and concomitant medication assessments summarized by treatment group and time point of collection, when appropriate.
Descriptive statistics (arithmetic mean, standard deviation (SD), coefficient of variation (CV), median, minimum, and maximum) will be calculated for quantitative safety data as well as for the difference from baseline, when appropriate.

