5.3 Sample Size Considerations

Approximately 413 subjects (177 in each active arm and 59 in placebo group) will be enrolled to obtain at least 392 mITT subjects (168 in each active treatment arm and 56 in placebo group) and to complete 350 PP subjects (150 in each active arm and 50 in placebo group). This sample size was calculated assuming that both active treatments would have equivalent success rates of 40% and placebo would have a success rate of 15%. This sample size will provide an overall probability of at least 0.9 of having the 90% Wald confidence interval, with Yates' continuity correction, of the difference between the test and reference success rates contained within the interval -0.20 to +0.20 in the PP population, in addition to establishing that the success rates for both active treatments are statistically greater than that of the placebo arm (two-sided continuity-corrected Z-tests, $\alpha = 0.05$) in the mITT population.

mITT (T:R:Placebo)	Prob. of Superiority*	of Superiority* PP (T:R:Placebo) Prob.		Prob. of study success
168:168:56 (392)	0.98	150:150:50 (350)	0.92	0.90

*) Superiority analysis based on two-sided, α = 0.05, continuity-corrected Z-tests.

**) Bioequivalence (BE) analysis based on 90% confidence interval (CI) of the difference between Test and reference for proportions of subjects with treatment success, calculated by the Wald's method with Yates' continuity correction.

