9.1.1 Bioequivalence Analysis

The efficacy bioequivalence of the test and reference treatments will be based on the proportions of subjects with clinical success. The hypothesis tested for clinical equivalence between test and reference will be:

Bioequivalence between the test and the reference product will be established if the 90% confidence interval for the difference in success proportions is contained within the equivalence limits [-0.20, +0.20].

In this case, the compound hypothesis to be tested is:

 $H_0: P_T - P_R < -0.2$ or $P_T - P_R > 0.2$ (meaning test product is not bioequivalent to the reference);

versus

 $H_a: -0.2 \leq P_T - P_R \leq 0.2$ (supporting bioequivalence);

where P_T = success proportion of test treatment, P_R = success proportion of reference treatment.

Let

- 1. n_T = sample size of test treatment group
- 2. $cn_T =$ number of subjects with success in test treatment group
- 3. n_R = sample size of reference treatment group
- 4. $cn_R =$ number of subjects with success in reference treatment group

$$\hat{P}_T = {cn_T / n_T}, \ \hat{P}_R = {cn_R / n_R},$$

Confidential

and
$$se = \left(\frac{\hat{P}_R(1 - \hat{P}_R)}{n_R} + \frac{\hat{P}_T(1 - \hat{P}_T)}{n_T} \right)^{1/2}$$

The 90% confidence interval will be estimated using Wald's method with Yates' continuity correction, as:

$$L = (\hat{p}_{T} - \hat{p}_{R}) - 1.645 \text{ se} - (1/n_{T} + 1/n_{R})/2$$
$$U = (\hat{p}_{T} - \hat{p}_{R}) + 1.645 \text{ se} + (1/n_{T} + 1/n_{R})/2$$

 H_0 will be rejected if $L \geq$ -0.20 and $U \leq 0.20$ resulting in accepting H_A and concluding bioequivalence of the two products.

Tthe following SAS code will be used to test bioequivalence:

```
proc freq data = dataset;
tables treat*outcome/ riskdiff (Equiv correct);
run;
```

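### One pair of planned success rates (40%/15%) serves both the PP and mITT sets with no allowance for the 42 subjects in mITT only; this is unsupported, probably optimistic, and lowers an overall success probability already short of 0.9

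*Protocol*

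**What the plan says.** Protocol 8.2, Table 5, plans 168:168:56 subjects in mITT and 150:150:50 in PP, gives 85% power, and attaches one footnote to both columns: "Sample sizes were calculated assuming: 40.0% success rate for active treatment, and 15.0% success rate for vehicle; 20% equivalency margin (EQ"). SAP 5.3 repeats the sizes, "assuming that both active treatments would have equivalent success rates of 40% and placebo would have a success rate of 15"%. It reports 0.98 for superiority (mITT), 0.92 for equivalence (PP) and 0.90 for study success.

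The two sets treat early leavers differently. Per the SAP synopsis, subjects who discontinue for any reason other than treatment failure are "excluded from the PP population, but included in the mITT population, using Last Observation Carried Forward (LOCF"). Protocol 8.1 and SAP 7.5.5 and 7.6.5 agree. Treatment-failure discontinuers stay in PP as failures.

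Clearance ends participation. The rule in the SAP synopsis (Study Design) opens "In case the primary endpoint is reached at any of the visits prior to the Day 28 visit, it will be considered as End of" and goes on to make that the subject's final visit; Protocol 3.1 is similar.

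The equivalence limits are those in Protocol 8.2: the interval must be "contained within the limits of -0.20 to +0.20". SAP 9.1.1 gives the method: "The 90% confidence interval will be estimated using Wald's method with Yates' continuity correction".

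**The concern.** The planned sets differ by 168 − 150 = 18 subjects in each active arm and 56 − 50 = 6 on vehicle, 42 in all. One pair of rates can describe both sets only if these 42 also clear at 40% and 15% on average. Neither document says so.

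The plan's rules point the other way for part of the group. A subject seen clear at a visit completes the study at that visit. A subject who discontinues will therefore normally have warts at the last observation, and LOCF carries that forward as a failure in mITT. The same subject is absent from PP. This pushes the mITT rate below the PP rate.

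Superiority of both actives over vehicle in mITT is required for study success and rests on a vehicle arm of 56. Its probability is therefore sensitive to the mITT rates assumed.

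**Working it through.** **Inputs.** Rates 40%/15%; PP 150:150:50; mITT 168:168:56 (Protocol 8.2, SAP 5.3). Equivalence: 90% Wald interval with Yates correction, limits ±0.20 (SAP 9.1.1). Superiority: continuity-corrected Z-tests, two-sided 0.05, each active against the shared vehicle arm (SAP 5.3, 9.1.2). SAP 9.1.2 refers back to the equivalence formulation, which uses an unpooled standard error (SE), but does not write the test out. Both SE forms are shown.

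**Step 1: reproduce the plan's figures at equal rates.**

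- Equivalence, normal approximation: se = √(2 × 0.40 × 0.60/150) = 0.0566; correction = (1/150 + 1/150)/2 = 0.0067. Power = 2Φ((0.20 − 0.0067)/0.0566 − 1.645) − 1 = 0.924. Exact enumeration gives 0.928. The SAP's 0.92 is reproduced.
- Superiority, one comparison, unpooled normal approximation: se = √(0.24/168 + 0.1275/56) = 0.0609; correction = (1/168 + 1/56)/2 = 0.0119. Power = Φ((0.25 − 0.0119)/0.0609 − 1.96) = 0.974, or 0.984 without the correction. The SAP's 0.98 corresponds to this single comparison. Exact figures are 0.940 (pooled) and 0.958 (unpooled) for one comparison, and 0.906 and 0.933 for both.
- Overall: 0.98 × 0.92 = 0.90, the SAP's figure. The exact joint probability, with PP nested in mITT and both actives against one vehicle arm, is 0.848 (pooled) or 0.871 (unpooled).

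**Step 2: derive the second set's rates.**

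- Case A, 40%/15% is the PP rate. If none of the 42 clear: active 0.40 × 150/168 = 35.7%, vehicle 0.15 × 50/56 = 13.4%. If they clear at half the PP rate: 0.40 × (150 + 9)/168 = 37.9% and 0.15 × (50 + 3)/56 = 14.2%.
- Case B, 40%/15% is the mITT rate. If none of the 42 clear, the PP rates are 0.40 × 168/150 = 44.8% and 0.15 × 56/50 = 16.8%.

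**Step 3: recompute.** Outcomes in the PP part and the mITT-only part are independent binomials. Success requires equivalence in PP and both superiority tests in mITT. Pairs are pooled / unpooled SE.

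| Scenario | Equivalence (PP) | Both superior (mITT) | Overall |
|---|---|---|---|
| Equal rates | 0.928 | 0.906 / 0.933 | 0.848 / 0.871 |
| A, mITT-only at half rate | 0.928 | 0.876 / 0.914 | 0.822 / 0.855 |
| A, mITT-only all failures | 0.928 | 0.843 / 0.894 | 0.793 / 0.837 |
| B, mITT-only all failures | 0.911 | 0.912 / 0.938 | 0.840 / 0.861 |

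**Step 4: what equal rates would require.** Suppose half of the 42 were LOCF failures. The other half would then have to clear at 0.40/0.5 = 80% on active and 0.15/0.5 = 30% on vehicle to keep the average at 40%/15%.

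**The case against.** A reader might infer that the two rates contradict each other. The documents do not support that. The mITT-only group is not made up of discontinuers alone: Protocol 8.1, SAP 7.5.3 and the shell of SAP Table 14.1.1.2 also remove subjects from PP for ineligibility, non-compliance, major deviations, restricted medication or visits outside the window. Such subjects may complete with clearance and count as mITT successes. Treatment-failure discontinuers remain in PP, those with no post-baseline visit are outside mITT, and the early termination visit includes a wart inspection that could find clearance. The split of the 42 is not given. All of this stands, and it is why the point is that equality is unsupported, not that it is impossible.

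A reader might also infer that the protocol's 85% is overstated. Protocol 8.2 describes only the equivalence test, "evaluated using a two-sided 90% confidence interval". Read that way, 85% is conservative against 0.91 to 0.93 in every scenario. Only if it meant overall success would the case A figures matter, and even then the unpooled half-rate figure (0.855) does not fall below it.

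Nor does the shared rate explain the whole gap to the SAP's 0.90. Most of that gap is present at equal rates.

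Finally, the SAP cites a note of February 2019 about site 201, so it was completed after trial conduct had begun, and a restated planning probability changes no test or decision rule. That limits the consequence. It does not make the stated 0.90 correct.

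**Conclusion.** The concern holds in a limited form. One pair of rates is applied to two sets that handle discontinuers differently, with no stated rate for the 42 subjects who separate them. Under the LOCF rule the assumption is probably optimistic for mITT.

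The SAP's overall probability of at least 0.9 is not reached in any scenario examined. The shortfall at equal rates is about 3 to 5 points (0.90 − 0.871 and 0.90 − 0.848). The shared rate adds about 1 to 5.5 points: 0.848 − 0.840 at the smallest (case B, pooled) and 0.848 − 0.793 at the largest (case A, all failures, pooled). On the unpooled SE, which SAP 9.1.2 appears to point to, the addition is 1.0 to 3.4 points. It would be zero if the mITT-only subjects cleared at the full rate. Equivalence power is barely affected.

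These sizes rest on assumed clearance rates for the mITT-only group (none, or half the PP rate), on the planned set sizes being met exactly, and on the two actives being truly equal.

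**What to change.** In Protocol 8.2 and SAP 5.3:

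1. State which population 40%/15% describes.
2. State an assumed success rate for the mITT-only subjects, with a range, and derive the other population's rates from it (for example 35.7%/13.4% in mITT if 40%/15% is the PP rate and none clear).
3. In SAP 5.3, restate the superiority (0.98) and overall (0.90) probabilities at those rates, requiring both actives to beat the shared vehicle arm, and name the SE used.
4. In Protocol 8.2, say whether the 85% is equivalence power or overall success.

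The cost is a recalculation and revised text in two paragraphs. Sample size, endpoint, populations and tests need not change. The downside is a less favourable stated probability, about 0.79 to 0.86 over the scenarios with reduced clearance, of which only the part set out above comes from the shared rate.
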